## IV. Outcomes

**Primary Outcome:** The primary outcome for the pilot trial will be the Verbally administered Numeric Rating Scale (VNRS) for clinical pain measurement (0-100) at 30 minutes following randomized medication administration. 

Secondary Outcomes: Secondary outcomes will include adverse events including hypoxia needing supplemental oxygen (SpO2 < 90%); hypotension (systolic blood pressure < 90mmHg); advanced airway or bag mask ventilation; incidence of nausea/vomiting/headache/dizziness requiring treatment; serial (30 minute intervals until ED discharge, up to 120 minutes or rescue narcotic administration) measurements of a) VNRS for clinical pain (0-100), b) Patient Global Assessment (PGA) of Pain Control, c) Richmond Agitation-Sedation Scale (RASS) scores, and d) time-weighted Summed Pain Intensity Difference (SPID); number of rescue narcotic doses at 30 minutes and during ED stay (up to 120 minutes); time to a reduction in VNRS pain score of 10 points; patient cognitive function as assessed by the Six Item Screener (SIS) at 30 minutes; Healthcare Professional Global Assessment (HPGA) of the method of pain control at 30 minutes; and acceptability of pain treatment to health care providers.

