## I. Objective and Specific Aims

Our objective is to perform a prospective, randomized, interventional trial of Emergency Department (ED) administration of DSUVIA versus standard care pain management comparing pain treatment outcomes in injured patients with moderate to severe pain.

**AIM #1:** To determine if, among injured patients with moderate to severe pain, treatment with DSUVIA compared to standard care pain treatment in the ED reduces the Verbally administered Numeric Rating Scale (VNRS) for clinical pain measurement (0-100) at 30 minutes.

Hypothesis #1: Null Hypothesis: There will be no difference in the pain score at 30 minutes of patients who received DSUVIA as compared to standard care pain medicine in trauma patients

**AIM #2**: To determine if, among injured patients with moderate to severe pain, treatment with DSUVIA compared to standard care pain treatment in the ED reduces adverse effects and events related to pain medication(s) including nausea/vomiting, headache, dizziness, hypoxia, hypotension, and need for advanced airway.

Hypothesis #2: Null Hypothesis: There will be no difference in the rate of adverse events of nausea/vomiting, headache, dizziness, hypoxia, hypotension and need for advanced airway in patients who received DSUVIA as compared to standard care pain medicine in trauma patients.

**AIM #3:** To determine if, among injured patients with moderate to severe pain, treatment with DSUVIA compared to standard care pain treatment in the ED improves pain treatment effectiveness including serial VNRS scores (every 30 minutes), the need for rescue narcotic administration, the time needed to reduce the VNRS pain score by 10 points, time-weighted summed pain intensity difference, patient global assessment (PGA), Six Item Screener (SIS) cognitive assessment and Richmond Agitation-Sedation Scale scores.

Hypothesis #3: Null Hypothesis: There will be no difference in the pain treatment effectiveness, need for rescue narcotic administration, time to reduction of 10 points of VNRS pain score by 10 points, the time-weighted summed pain intensity difference, patient global assessment, Six-Item Screener and the Richmond Agitation-Sedation Scale scores in patients who received DSUVIA as compared to standard care pain medicine in trauma patients.

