#### Secondary Outcome Definitions:

**Hypoxia, hypotension or need for advanced airway:** The principal safety outcome for the trial will be the incidence of serious adverse events following the first dose of analgesic following randomization including hypoxia (SpO2 < 90%), hypotension (SBP < 90 mmHg) or the need for advanced airway management (placement of an endotracheal tube, supraglottic airway or bag mask ventilation) until ED discharge (up to 120 minutes), when feasible.

Composite outcome of nausea, vomiting, headache, and/or dizziness requiring treatment: The incidence of nausea, vomiting, headache, and/or dizziness requiring treatment will be recorded for initial 30 minutes, when feasible.

Verbally administered Numeric Rating Scale (VNRS) pain measurements (0-100) at 30- minute intervals: VNRS for clinical pain (0-100) measurements at approximate 30-minute intervals until discharge from the ED (up to 120 minutes) or rescue narcotic administration, will be obtained when feasible.

**Patient Global Assessment (PGA) of Pain Control at 30-minute intervals:** The PGA of the method of pain control at approximate 30-minute intervals until discharge from the ED (up to 120 minutes) or rescue narcotic administration, will be obtained when feasible. The research team will read the following statement aloud to the subject and the response will be recorded: "Overall, would you rate this method of pain control during the last 30 minutes/hours as being poor (1), fair (2), good (3), or excellent (4)?"

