## IX. Human Subjects

We anticipate that this study will be conducted utilizing a written informed consent while the patient resides in the ED.

Study Risks and Benefits: Risks associated with pain management include allergic reaction, hypoxia requiring oxygen, (SPO2 < 90%), hypotension (SBP < 90 mmHg), or need for advanced airway management (placement of an endotracheal tube or supraglottic airway) following medication administration.

Regardless of treatment arm, we anticipate that enrolled subjects will benefit from increased monitoring of primary and secondary outcomes, specifically, a focus on adequate pain control and pain management complications including respiratory compromise, hypotension, decreased sensorium, and need for advanced airway control.

Institutional Review Board: A central IRB at the University of Pittsburgh will be utilized for the regulatory needs of studies. All current LITES Network sites have IRBs which have experience and engagement with central IRB procedures.

Training and Participating Site Coordination: As the clinical coordinating center for the trial, the University of Pittsburgh (LITES) at the University of Pittsburgh will be collaboratively responsible for all research coordinator training, provider training. Research coordinators, providers and associated staff will be trained during the months prior to the trial start date regarding the scientific basis for the study, specific inclusion and exclusion criteria, study procedures and SOPs. Training verification and retraining will occur if new staff is hired at individual participating sites.

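### Hypoxia and the four symptoms are worded inconsistently for Aim 2, and the treatment-conditioned wording lets unmasked treating decisions enter the safety comparison

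*Combined protocol and SAP*

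**What the plan says.** Hypoxia. The list of secondary outcomes in section IV counts "hypoxia needing supplemental oxygen (SpO2 < 90" percent). The principal safety outcome, under Secondary Outcome Definitions, covers events "including hypoxia (SpO2 < 90%), hypotension (SBP < 90 mmHg) or the need for advanced airway management", with no mention of oxygen. The risk text in section IX returns to the conditioned form, "hypoxia requiring oxygen, (SPO2 < 90" percent). The Aim 2 text in sections I and VI says only hypoxia.

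Four symptoms. The section IV list counts the "incidence of nausea/vomiting/headache/dizziness requiring treatment". The matching definition keeps the treatment condition and limits recording to the first 30 minutes. The Aim 2 null hypothesis in section I is that there is "no difference in the rate of adverse events of nausea/vomiting, headache, dizziness, hypoxia, hypotension and need for advanced airway", without a treatment condition. The Aim 2 analysis in section VI repeats the unconditioned list and applies chi-square tests to the composite of any event and to each event separately.

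Masking. Section III says that trauma attending and ED physicians are not masked, and that the arm is concealed from outcome assessors for follow-up. I found no criteria for when a symptom or a desaturation requires treatment.

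**The concern.** A patient who is nauseated but given nothing is an event under the Aim 2 hypothesis and a non-event under the outcome definition. A patient whose saturation falls to 87% and recovers without oxygen is an event under the principal safety outcome, and may not be one under the section IV list. Two analysts following the plan in good faith could report different Aim 2 rates.

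The conditioned wording also has a problem of its own. When treatment is part of the event, the count is the product of how often the symptom occurs and how readily it is treated. Clinicians who know the arm may treat the same complaint more readily in one arm than in the other. Concealing the arm from assessors does not help, because the decision has already been made at the bedside. Aim 2 asks about adverse effects of the medication, and a treated-only count mixes these with prescribing behaviour. The mixture could create a difference or hide one.

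**Working it through.** The plan gives no event rate, power or sample size for Aim 2, so there is no figure to reproduce. The check has two parts.

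**1. Wording side by side**

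| Component | Section IV list | Secondary Outcome Definitions | Aim 2 hypothesis and analysis |
|---|---|---|---|
| Hypoxia | SpO2 < 90%, needing oxygen | SpO2 < 90% | named only |
| Four symptoms | requiring treatment | requiring treatment, first 30 minutes | named only, no condition |
| Hypotension | SBP < 90 mmHg | SBP < 90 mmHg | named only |
| Airway | advanced airway or bag mask ventilation | tube, supraglottic airway or bag mask ventilation | advanced airway, undefined |

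The two outcome texts agree on hypotension and airway support. They differ in wording on hypoxia. For the symptoms they agree with each other, and the Aim 2 text lacks their condition.

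**2. Hypothetical illustration for the symptom endpoint**

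Inputs from the plan: 75 per arm, and a two-sided 5% level (stated in section VI for Aim 1 and borrowed here). Assumed inputs: a symptom rate s, equal in both arms, and treated fractions t1 and t2.

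Recorded rate in arm i: p_i = s × t_i.

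Normal approximation to the rejection probability: Φ[(|p2 − p1| − 1.96 × S0) / S1], with p̄ = (p1 + p2)/2, S0 = √[2p̄(1 − p̄)/75] and S1 = √{[p1(1 − p1) + p2(1 − p2)]/75}.

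Example with s = 30%, treated 50% vs 70%: p1 = 0.15, p2 = 0.21, S0 = 0.0627, S1 = 0.0625. The argument is (0.06 − 1.96 × 0.0627)/0.0625 ≈ −1.01, which gives about 16%.

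The table gives exact rejection probabilities, found by summing the binomial probabilities of all outcomes that the uncorrected chi-square test rejects.

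| Symptoms, both arms | Treated | Recorded | False rejections |
|---|---|---|---|
| 30% | 50% vs 50% | 15% vs 15% | about 5% |
| 30% | 50% vs 60% | 15% vs 18% | about 8% |
| 30% | 50% vs 70% | 15% vs 21% | about 16% |
| 40% | 40% vs 60% | 16% vs 24% | about 23% |

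With 50% vs 70% treated, the figure runs from about 8% at a symptom rate of 10% to about 21% at 40%. If any occurrence is counted instead, it stays at about 5% in every row, because the symptom rates are equal by assumption. The plan does not say whether the chi-square test is continuity-corrected. With the correction (1/75 subtracted from the absolute difference in proportions), the last row falls from 23% to about 17%.

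**The case against.** The strongest reply is that definitions belong in the definitions section. On the symptoms, that section and the section IV list agree. The Aim 2 text is a summary: it gives no threshold for hypotension either, and nobody would call that a conflict. On hypoxia, the parenthesis in the section IV list may simply say what hypoxia needing oxygen means, in which case the two texts coincide. The principal safety outcome already uses the objective threshold. A treatment condition can also serve as a reasonable severity filter. Finally, scripted questions answered by patients who know what they received replace some treating bias with reporting bias.

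Much of this stands. It makes hypoxia an ambiguity rather than a proven contradiction, and it means that a cross-reference would settle part of the symptom problem. It does not remove the dependence of the treated-only count on unmasked decisions, because the definitions section itself contains that condition.

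A reader might go further on three points that the documents do not support:

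- **Airway support as a third conflict.** Both outcome texts count bag mask ventilation; the definition reads "placement of an endotracheal tube, supraglottic airway or bag mask ventilation". The narrower "placement of an endotracheal tube or supraglottic airway" appears only in the section IX risk description, which defines no endpoint. Both versions also depend on a clinician's decision, so choosing between them would not remove that dependence.
- **Double counting of headache treatment as rescue.** The rescue outcome is headed and listed as doses of narcotic, so a non-narcotic given for headache would not plainly count. One dose informing two secondary outcomes is not in itself an error.
- **A large bias as a finding.** The documents do not show that treating behaviour differs by arm. The higher figures need assumed gaps of 20 points; a 10-point gap gives about 8%.

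**Conclusion.** The point holds in limited form. The Aim 2 text omits the treatment condition that the outcome definitions attach to the four symptoms, and the hypoxia wording is ambiguous between the outcome list and the principal safety outcome. The plan does not say which version is analysed.

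Because the trial is open label, the treated-only symptom count can differ between arms with no difference in symptoms. Under the assumed rates, false rejection runs from about 8% with a 10-point gap in treating to about 16% to 23% in the 20-point examples, against about 5% with equal treating. These figures rest wholly on assumed symptom rates and treated fractions. They cover the symptom endpoint only, and say nothing about hypoxia, airway support or the any-event composite. Even with equal treating, the treated-only count lowers the recorded rate to the treated share of cases.

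The primary outcome and its analysis are unaffected. The change is worth making because all of Aim 2, including the declared principal safety outcome, draws on these definitions.

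**What to change.** - Use recorded SpO2 < 90%, whether or not oxygen is given, as the hypoxia outcome in the section IV list, the Secondary Outcome Definitions and the Aim 2 analysis.
- Record nausea, vomiting, headache and dizziness as present or absent with a scripted question at the existing 30-minute assessment, where the research team already reads the PGA item aloud.
- Analyse any occurrence in Aim 2 and report events requiring treatment as a subset. The sponsor's present endpoint is kept as that subset.
- Have the Aim 2 analysis refer to the Secondary Outcome Definitions, and state there that bag mask ventilation counts as airway support.

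The cost is some rewording and a few yes/no questions. These changes concern outcome recording and alter no care. There are three downsides: absolute rates will rise in both arms, some headache or dizziness caused by the injury will be counted and may dilute a drug effect, and patient-reported symptoms in an open-label trial still carry some reporting bias.

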#### Secondary Outcome Definitions:

**Hypoxia, hypotension or need for advanced airway:** The principal safety outcome for the trial will be the incidence of serious adverse events following the first dose of analgesic following randomization including hypoxia (SpO2 < 90%), hypotension (SBP < 90 mmHg) or the need for advanced airway management (placement of an endotracheal tube, supraglottic airway or bag mask ventilation) until ED discharge (up to 120 minutes), when feasible.

Composite outcome of nausea, vomiting, headache, and/or dizziness requiring treatment: The incidence of nausea, vomiting, headache, and/or dizziness requiring treatment will be recorded for initial 30 minutes, when feasible.

Verbally administered Numeric Rating Scale (VNRS) pain measurements (0-100) at 30- minute intervals: VNRS for clinical pain (0-100) measurements at approximate 30-minute intervals until discharge from the ED (up to 120 minutes) or rescue narcotic administration, will be obtained when feasible.

**Patient Global Assessment (PGA) of Pain Control at 30-minute intervals:** The PGA of the method of pain control at approximate 30-minute intervals until discharge from the ED (up to 120 minutes) or rescue narcotic administration, will be obtained when feasible. The research team will read the following statement aloud to the subject and the response will be recorded: "Overall, would you rate this method of pain control during the last 30 minutes/hours as being poor (1), fair (2), good (3), or excellent (4)?"

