#### **Richmond Agitation-Sedation Scale (RASS) score at 30-minute intervals:**

A RASS score at approximate 30-minute intervals until discharge from the ED (up to 120 minutes) or rescue narcotic administration, will be obtained when feasible. (-5 to 4+; 10-point scale).

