The DSMB will review the primary and secondary outcomes bi-annually. Prior to initiation of the trial, the final monitoring plan will be developed to serve as the guide to the DSMB's decision-making process concerning early stopping of the trial. The interim analysis will consist of two components, efficacy evaluation and futility evaluation. The purpose of the efficacy evaluation is to detect early sign of treatment effect early in the study. The purpose of the futility analysis is to assess if the study is unlikely to achieve a statistically significant effect. In making the decision to recommend termination of the study, the DSMB shall be guided by several types of information: (i) a formal stopping rule based on the primary analysis (comparison of treatment groups on the primary outcome), (ii) information on safety outcomes by treatment group, (iii) consistency between results for primary and secondary outcomes, (iv) consistency of treatment effects across subgroups, and (v) conditional power.

We have designed this trial with one-interim analyses before the final analysis. The number of interim analyses will be finalized in discussion with the DSMB prior to the initiation of the study. The interim analysis plan is based on the Lan and Demets approach utilizing an O'Brien-Fleming spending function to

determine alpha spending and test boundaries. A formal interim analysis of efficacy will be performed when 50% of the randomly assigned participants have completed the assessment of the primary outcome. We will use a t-test to test for difference. The level of significance will maintain an overall p-value of 0.05 according to O'Brien-Fleming stopping boundaries leaving a p value of 0.003 and 0.049 for the interim and final analyses, respectively. This translates to a two-sided z-value for the interim and final analyses of +/-2.96 and +/-1.97, respectively.

In addition, the futility of the study will be evaluated at the time an interim efficacy test is conducted. Specifically, the conditional power will be calculated. If the condition power is less than value prespecified by the DSMB (e.g., <20%), we can conclude that it would be futile to continue with the investigation.

Surveillance for Outcomes and Data Elements: Data will be collected prospectively as patient care progresses. This will include a review of the prehospital patient care report(s), ED and electronic/ paper hospital records.

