In-Hospital Resuscitation Elements: Demographics, prehospital assessments and narcotic treatments, injury mechanism and characteristics, ED vitals, ED procedures/interventions, injury severity, injury severity scoring and assessment, ICU days and length of stay.

Data Entry: The DCC will create web-based HTML forms to collect necessary information from all participating sites. Web entry forms will have dynamic features such as edit and data type checks. Details and clarification about data items will be provided using pop-up windows. Data encryption and authentication methods will be used. Additional features will be built into the web entry forms including: forms transmission history, access to past forms, tracking of data corrections, and the capability to save and re-load incomplete forms. The subjects will be identified by a study number only. All clinical interventions will become part of the patient's medical records. All hard copy source documentation will be kept in a secure location for the time frame designated by each participating site's requirements. The electronic data will be entered and maintained on a password protected SSL website designed for this trial.

The data entered for the DEEP trial will be maintained by the DCC on a relational database. The database would be housed in a virtual environment so in the event of a hardware failure it would migrate to a new host. The data will be backed on a regular schedule with full transaction log files in use and copies of the data will be stored offsite with a secure service. In addition to the data server, the production web server will also be backed up routinely and as a virtual machine can be transitioned to different hardware automatically in case of hardware failure. All Servers are behind an enterprise firewall and access has to be granted through the firewall even within the University Network.

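### The principal safety outcome uses SpO2 and SBP thresholds with no common reading times, so any difference in charting frequency between open-label arms would distort the comparison

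*Combined protocol and SAP*

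**What the plan says.** Under Secondary Outcome Definitions, the principal safety outcome is the incidence of serious adverse events after the first post-randomization analgesic dose, including "hypoxia (SpO2 < 90%), hypotension (SBP < 90 mmHg) or the need for advanced airway management" (bag mask ventilation counts as airway management). Observation runs "until ED discharge (up to 120 minutes), when feasible".

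The same section gives VNRS, PGA, RASS and SPID approximate 30-minute times, ending at ED discharge, 120 minutes or rescue narcotic. No section says when, how often or by what method SpO2 and blood pressure are read. Section VI, under Surveillance for Outcomes and Data Elements, says "Data will be collected prospectively as patient care progresses", with review of records. The In-Hospital Resuscitation Elements list "ED vitals, ED procedures/interventions" without a frequency.

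The trial is open label (section III), and trauma attending and ED physicians are unmasked. Assignment is concealed from outcome assessors for follow-up. Aim 2 in section VI compares event proportions by chi-square, then by logistic regression on site and unbalanced baseline characteristics.

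Two further passages bear on the point. The Secondary Outcomes paragraph of section IV words hypoxia as "hypoxia needing supplemental oxygen (SpO2 < 90" (per cent), which is narrower than the later definition. Section IX, Human Subjects, says that, regardless of arm, "we anticipate that enrolled subjects will benefit from increased monitoring of primary and secondary outcomes".

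**The concern.** The chance of recording at least one value below a threshold rises with the number of values recorded. Here that number is left to bedside practice under known assignment. One arm receives a single study tablet and the other standard care without a fixed regimen, so practice could differ. Staff might watch the study drug more closely, or might check vital signs at each standard-care dose. These possibilities push in opposite directions.

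Concealment from follow-up assessors cannot equalise readings already charted at the bedside. The logistic model has no term for number of readings or time observed. A difference in charting could therefore appear as a drug effect or hide one. This touches the Aim 2 conclusion and also the DSMB, whose termination recommendation is guided partly by safety outcomes by arm (section VI, Interim Analyses). Analysts cannot restore readings that were never taken.

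**Working it through.** **No plan figure to reproduce.** The sample size rests on Aim 1 only. The documents give no event rate, power or reading frequency for the safety outcome.

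**Input from the documents.** 75 patients per arm (section VI, Sample Size).

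**Assumptions.** The true rate q is the same in both arms. An affected patient has one 10-minute dip, starting uniformly between 0 and 110 minutes. The dip is recorded only if a reading falls inside it. One arm is charted every 30 minutes and the other every 15, up to 120 minutes. The test is the two-sided 5% pooled chi-square.

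**Step 1: share of dips caught.** A reading at time t catches a dip that starts in the 10 minutes before t. The reading at 120 minutes catches none, because no dip starts after 110.
- 30-minute charting: readings at 30, 60 and 90 count, so 3 × 10/110 = 27.3%.
- 15-minute charting: readings at 15, 30, …, 105 count, so 7 × 10/110 = 63.6%.
- Ratio of recorded rates: 63.6/27.3 = 2.3, whatever q is.

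**Step 2: false-positive rate.** Recorded rates are 0.273q and 0.636q. Rejection is summed exactly over two binomial arms of 75.

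| True rate, both arms | Recorded, 30 min | Recorded, 15 min | Chi-square significant |
|---|---|---|---|
| 1% | 0.3% | 0.6% | 0.1% |
| 2% | 0.5% | 1.3% | 1.1% |
| 3% | 0.8% | 1.9% | 3.1% |
| 5% | 1.4% | 3.2% | 8.3% |
| 10% | 2.7% | 6.4% | 17.6% |
| 20% | 5.5% | 12.7% | 34.9% |

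At low rates the test seldom rejects because few events are expected: at 1%, 75 × 0.0027 = 0.2 and 75 × 0.0064 = 0.5 per arm. The 2.3-fold distortion of the recorded rates remains.

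**Step 3: a second model.** Suppose each reading independently falls below threshold with probability r, so that P(at least one of k) = 1 − (1 − r)^k. With r = 0.01 and 8 versus 4 readings:
- 1 − 0.99^8 = 7.7%
- 1 − 0.99^4 = 3.9%
- ratio 1.96, significant in 16.5% of trials.

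With 4 readings in both arms and r = 0.01, 0.02 or 0.05, rejection is 4.7%, 5.3% and 5.1%. Equal reading removes the distortion.

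**Step 4: should scheduled readings replace all events?** Take a true difference of 5% versus 20%. With every dip captured, power at 75 per arm is 83%. With 30-minute readings only, the recorded rates are 0.273 × 5% = 1.4% and 0.273 × 20% = 5.5%, and power falls to 26%. Scheduled readings are therefore too insensitive to carry the main comparison.

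**The case against.** Four objections have force.

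1. **Unequal charting is not shown.** A reader might infer that the arms will be read unequally, or that the bias favours a particular arm. The documents support neither. The only statement about monitoring, in section IX, anticipates more of it in both arms and names respiratory compromise and hypotension. It makes a large gap less likely, but it sets no schedule and does not secure equality.

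2. **Not every low reading is clearly an event.** The Secondary Outcomes paragraph ties hypoxia to a need for supplemental oxygen, and the risk statement in section IX is similar. Under that wording a brief dip that needs no oxygen would not count, and the dip model fits hypoxia less well. The later definition omits the oxygen condition, so the outcome is open to both readings. Airway events depend much less on reading frequency.

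3. **Events may be rare.** Section II cites less than 1% for respiratory depression and hypoxia with sufentanil, and section X expects relatively few serious adverse events. At true rates of 1% to 3% the false-positive rate stays below 5%. The higher figures should not be taken as typical. However, the documents give no rate for hypotension in injured patients, which could be higher.

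4. **This is a secondary outcome in what section IV calls a pilot trial.** That limits the consequence, but the protocol itself makes it the principal safety outcome.

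Continuous recording of SpO2 would also shrink the hypoxia part of the problem. The documents do not specify it.

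**Conclusion.** The concern holds as a conditional weakness in ascertainment. Two components of the principal safety outcome depend on reading frequency, that frequency is not standardised, treating physicians are unmasked, and Aim 2 makes no allowance for it. Unequal time to ED discharge would act in the same way.

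If charting differs as assumed (every 30 versus every 15 minutes, one 10-minute dip), recorded rates differ 2.3-fold at equal true risk. The false-positive rate runs from about 0.1% at a 1% true rate to about 35% at 20%. It exceeds the nominal 5% at the tabulated true rates of 5% and above. All of these rates, dip lengths and charting intervals are assumptions. The documents establish neither that a difference in charting will occur nor its direction. The change is still worth making, because it is cheap now and the missing readings cannot be recovered later.

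**What to change.** 1. In Secondary Outcome Definitions, have research staff record the displayed SpO2 and SBP before dosing and at each 30-minute study assessment, to 120 minutes or ED discharge. Do this in both arms and continue after rescue narcotic, because the safety window does not stop there.
2. Keep the principal safety outcome and the Aim 2 comparison on all events, with advanced airway and bag mask events retained.
3. Add a prespecified sensitivity comparison of hypoxia and hypotension that uses the scheduled readings only.
4. Report the number of charted readings and the time observed, by arm.
5. Reconcile the two wordings of hypoxia in section IV so that a single event definition applies throughout.

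**Cost.** Two form fields at assessments already planned, a few added readings after rescue when the other serial assessments stop, and some SAP wording. The scheduled-only analysis misses many short dips (it catches 27% in the model above), which is why it is a sensitivity analysis. The existing assessments are approximate and done when feasible, so equal readings are not guaranteed, and the counts in item 4 will show how close the arms came. Clinical monitoring is unchanged.
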